4.1 Analysis Populations

Three analysis populations will be used to summarize the results from this study.

Safety Population: All subjects who receive at least 1 administration of investigational product (ciraparantag or placebo).

Pharmacokinetic (PK) Population: All subjects who receive at least 1 administration of study drug, and provide sufficient data to estimate at least one PK parameter without protocol deviations with potential to affect these measurements.

Pharmacodynamic (PD) Population: All subjects who receive at least 1 administration of investigational product, and provide at least one on-treatment WBCT measurement without protocol deviations with potential to affect these measurements.

The frequency and percentage of subjects in each population will be summarized by group. Subjects who are excluded from the analysis populations will be listed by group and subject.

4.2 Study Subjects

4.2.1 Subject Disposition

Subject disposition will be summarized using the number of all screened subjects, the number and percent (of screened) of subjects randomized and the reasons for not being randomized, the number and percent (based on subjects randomized) of subjects who complete the study, and the number and percent (based on subjects randomized) of subjects who discontinue the study and the reasons for discontinuation. Subject disposition and completion status will be listed for all screened subjects.

Eligibility status for the study will be listed for all screened subjects.

4.2.2 Protocol Deviations

Protocol deviations will be identified prior to database lock and may include but are not limited to: significant violations of inclusion/exclusion criteria, noncompliance with the study treatment taken, the use of restricted medications or not following clinical trial protocol procedures that may affect evaluation of the PD or PK profiles.

All protocol deviations will be listed by subject and summarized by deviation type.

4.3 Subject Demographics and Other Baseline Characteristics

Demographic and baseline characteristics will be summarized by each treatment. The demographic and baseline characteristics will consist of age, gender, race, ethnicity, height (cm), weight (kg), and body mass index (BMI) (kg/m^2). Individual demographic and baseline characteristics will be listed by subject.

The age is a calculated parameter. Age will be calculated using the subject's date of birth and the subject's informed consent date. Continuous variables (age, height, weight, BMI) will be summarized by n, mean, SD, min, median, and max. Number of subjects and percentages will be used to describe categorical (discrete) variables (age group, gender, race and ethnicity).

4.4 Medical/Surgical History and Procedures/Non-Drug Therapies

The presence/absence of any current medical condition and/or other significant medical/surgical history will be coded using Medical Dictionary for Regulatory Activities (MedDRA) Version 20.0, or higher. Any procedures/non-drug therapies will also be coded using MedDRA or World Health Organization (WHO) Drug Enhanced Dictionary (March 2017 or later), as appropriate.

Medical/surgical history will be summarized by treatment, and listed by subject. Procedures/non-drug therapies will be summarized by treatment, and listed by subject.

4.5 Prior and Concomitant Medications

All prescription medications and over-the-counter (OTC) products, including herbal products, taken in the 30 days prior to dosing or during the study period will be documented in the subject's source documentation and the eCRF.

Concomitant medication is defined as any medication other than the trial product that is taken on or after the first dose of apixaban (i.e., stop date is missing or is after the date of the first dose of apixaban). Details of all medications must be recorded at trial entry. Any changes in concomitant medications must be recorded at each visit. The information collected for each concomitant medication includes dosage, route, start date, stop date (or continuing) and indication. Prior medications will be recorded at the screening visit and will be defined as those medications with start and end date prior to first dose of apixaban. Concomitant medications will be defined as those medications with a stop date after the first dose of study drug or with a missing stop date. Prior and concomitant medications will be coded using the World Health Organization (WHO) Drug Enhanced Dictionary (March 2017 or later).

Prior and concomitant medications will be summarized by treatment including Anatomical Therapeutic Chemical (ATC) classification, preferred term and reported term. Medications will also be listed by subject.

4.6 Pharmacokinetic Analysis

4.6.1 Plasma and Serum Concentrations

Blood samples for PK assessment of ciraparantag and its metabolite BAP, and apixaban, will be analyzed using Liquid Chromatography/Mass Spectrometry (LC/MS) assay

methodology. Blood samples will be analyzed by the Bioanalytical Services department of [REDACTED] to obtain serum concentrations of ciraparantag and its metabolite, and plasma concentrations of apixaban. Serum and plasma concentrations will be listed at each time point by subject, and summarized by treatment at each time point using descriptive statistics (n, mean, SD, geometric mean, coefficient of variation (CV%), median, min and max values). Values below the quantification limit (BQL) will be treated as “0” in the summary statistics. Descriptive statistics that are not quantifiable will be designated as ‘NC’ in the summaries and a footnote added, NC = not calculable.

Plots of mean concentration levels of ciraparantag and its metabolite, and apixaban versus time will be generated for each treatment. Plots of individual subject’s concentration levels of ciraparantag and its metabolite, and apixaban versus time will also be generated.

4.6.2 Pharmacokinetic Parameters

PK calculations will be performed based on actual time of blood sample collection, using noncompartmental methods, using Phoenix WinNonlin (Version 6.3 or higher, Certara, Princeton, NJ). Values of BQL are set to 0 if they occur prior to the first or after the last quantifiable concentration, and are set to missing for data points in between.

PK parameters for ciraparantag (PER977) and BAP are displayed in [Table 2](#), and PK parameters for apixaban will include C_{max} , T_{max} , $AUC_{(0-last)}$, $t_{1/2}$, K_{el} , CL/F and V_z/F , if data allow. The PK parameters will be listed by subject and summarized by treatment using descriptive statistics (n, mean, geometric mean, median, and inter-quartile range (Q1:Q3), SD, CV%, min, and max). T_{max} and t_{last} will be described using n, min, 25th percentile, median, 75th percentile, and max.

Table 2 Parameters for Serum Ciraparantag (PER977) and BAP

Parameter	Units	Description
C_{max}	ng/mL	Maximum concentration in the sampled matrix, obtained directly from the observed concentration versus time data
C_{24}	ng/mL	Observed quantifiable analyte concentration in the sampled matrix at the 24-hour time point
C_{last}	ng/mL	Last observed quantifiable analyte concentration in the sampled matrix
t_{last}	h	Time of C_{last} , obtained directly from the observed concentration versus time data
T_{max}	h	Time of C_{max} , obtained directly from the observed concentration versus time data
$AUC_{(0-last)}$	ng·h/mL	The area under the concentration-time curve, from time zero to the last quantifiable concentration (C_{last})

$AUC_{(0-\infty)}$	ng·h/mL	Area under the concentration-time curve in the sampled matrix from zero (pre-dose) extrapolated to infinite time by addition of the last quantifiable concentration divided by the elimination rate constant: $AUC_{(0-\text{last})} + C_{\text{last}}/\lambda_z$
$\lambda_z (K_{el})$	1/h	Apparent terminal rate constant
$t_{1/2}$	h	Apparent terminal half-life, determined as $\ln(2)/\lambda_z$
CL	L/h	Systemic clearance after IV dosing, calculated for PER977 only
V_z	L	Volume of distribution after IV dosing, calculated for PER977 only
V_{ss}	L	Steady-state volume of distribution after IV dosing, calculated for PER977 only
$MR_{C_{\text{max}}}$		Metabolite to parent (BAP/PER977) ratio of C_{max}
$MR_{AUC(0-\text{last})}$		Metabolite to parent (BAP/PER977) ratio of $AUC_{(0-\text{last})}$
$MR_{AUC(0-\infty)}$		Metabolite to parent (BAP/PER977) ratio of $AUC_{(0-\infty)}$

The $MR_{C_{\text{max}}}$, $MR_{AUC(0-\text{last})}$, and $MR_{AUC(0-\infty)}$ are molecular weight corrected molar ratios of metabolite/parent.

The following PK parameters for ciraparantag (PER977) and its metabolite, BAP (Table 3), will be calculated for diagnostic purposes and listed, but will not be summarized.

Table 3 Listing Parameters for Serum Ciraparantag (PER977) and BAP

$t_{1/2}$, Interval	The time interval (h) of the log-linear regression to determine $t_{1/2}$
$t_{1/2}$, N	Number of data points included in the log-linear regression analysis
Rsq	Goodness-of-fit statistic for calculation of λ_z (regression coefficient)
$\%AUC_{\text{ex}}$	Percentage of $AUC_{(0-\infty)}$ that is extrapolated from t_{last} to infinity, calculated as: $100 \times [1 - (AUC_{\text{last}}/AUC_{0-\infty})]$, where t_{last} is the time of the last measurable serum drug concentration

4.6.3 Dose Proportionality

The dose proportionality of exposure PK parameters for PER977 and BAP ($AUC_{(0-\infty)}$, $AUC_{(0-\text{last})}$, and C_{max}), over the administered dose range will be investigated using the following power model:

$$\log (\text{PK parameter}) = a + b \times \log (\text{Dose})$$

Dose proportionality will be assessed statistically using the above power model approach with the logarithm of PK parameters as the dependent variables and the logarithm of the dose as the independent variable for subjects who receive one dose at a given dose

interval. The intercept (a) and the slope (b) together with their 90% confidence interval (CI) will be estimated and summarized for each PK parameter. Parameters ‘a’ and ‘b’ will be estimated using an ordinary least-squares approach or the equivalent. Dose proportionality will be declared if the 90% CI for the slope parameter ‘b’ lies entirely within the critical region (0.80, 1.25).

In addition, the dose proportionality of exposure PK parameters for PER977 and BAP ($AUC_{(0-\text{inf})}$, $AUC_{(0-\text{last})}$, and C_{\max}) will be evaluated between adjacent means using an ANCOVA model. The ANCOVA model for the log-transformed PK parameters (separate model for PER977 and BAP) will include dose (categorical) and gender as fixed effects, and weight as a covariate. A summary of the results of the ANCOVA, and pairwise comparisons by analyte including the dose ratio (%), exposure ratio (%), and 90% confidence interval will be presented.

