#### 1.2.4 PER977-02-001

PER977-02-001 was a randomized single-blind sequential group ascending ciraparantag reversal dose study in healthy volunteers who received a single dose of 60 mg edoxaban in the morning on Days 1-4 followed on Day 3 and Day 4 by a single IV dose of study drug. Five dose cohorts of 15 mg, 30 mg, 60 mg, 180 mg, and 360 mg ciraparantag (25 mg, 50 mg, 100 mg, 300 mg, and 600 mg ciraparantag acetate), respectively were planned and completed. Any subject who did not have a minimum increase in WBCT of 25% above baseline at the pre-study drug time point on Day 3 was discontinued from the study and replaced.

The pharmacokinetic results show that following 10-minute IV injection of ciraparantag on Day 3 and Day 4, serum PER977  $C_{max}$  were typically observed at 0.25 hour (i.e., at the first postdose time point measured five minutes after the end of the 10-minute injection). Ciraparantag was then rapidly eliminated, with mean half-life ( $t_{1/2}$ ) ranging from 0.207 to 0.336 hour (12.4 to 20.2 minutes). Clearance and volumes of distribution remained relatively constant across most doses and on both Days 3 and 4. Over the 24-fold dose range from 15 mg to 360 mg, ciraparantag  $C_{max}$  and total exposures ( $AUC_{(0-\infty)}$  and  $AUC_{(0-last)}$ ) increased approximately proportionally to the dose increase. However, the 90% confidence interval (CI) of the slope for Day 4  $AUC_{(0-last)}$  were completely above the predefined (0.9298, 1.0702) critical region; and the upper bounds of the 90% CI of the

slopes for other exposure parameters on Day 3 and Day 4 were just above the upper limit of the critical region. Dose-proportionality thus could not be statistically concluded.

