## 2 STUDY OBJECTIVES

The objectives of this Phase 2 study are:

- To evaluate the efficacy of ciraparantag in the reversal of anticoagulation induced by apixaban 10 mg BID (Q12) at steady state as assessed by WBCT
- To evaluate the safety and tolerability of ciraparantag 60 mg (100 mg), 120 mg (200 mg), and 30 mg (50 mg), and additional cohorts if necessary approximately administered 3 hours after 10 mg apixaban administration at steady state.
- To assess the PK characteristics of apixaban and ciraparantag and its primary metabolite

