## **5.9 Dose Escalation/De-Escalation**

Review of WBCT results, AEs, clinical laboratory tests, and ECG data will be conducted by a group that includes the Principal Investigator, Medical Monitor(s), and representative(s) of the Sponsor. The group will be responsible for the decision to expand a given dose cohort, escalate (or de-escalate) to a different dose from the planned dose, or stop the study. All meetings will be documented with minutes.

The goal of the study is to explore the dose range of ciraparantag that reverses the anticoagulation induced by therapeutic doses of apixaban at steady state. The study is intended to establish a dose of ciraparantag that fully reverses steady-state apixaban, to evaluate at least one dose above the reversal dose to establish a therapeutic index, and at least one partial or no effect dose.

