### 9.6 Dose Proportionality

The dose proportionality of exposure PK parameters for PER977 and BAP (AUC(0-inf), AUC(0-last), and Cmax), over the administered dose range will be investigated using the following power model:

log (PK parameter) = a + b \* log (dose)  
where 'a' is the intercept and 'b' is the slope.

Dose proportionality will be assessed graphically and statistically using the above power model approach with the logarithm of PK parameters as the dependent variables and the logarithm of the dose as the independent variable for subjects who receive one dose at a given dose interval. The intercept (a) and the slope (b) together with their 90% CI will be estimated and presented for each PK parameter. Parameters 'a' and 'b' will be estimated using an ordinary least-squares approach or the equivalent. Dose proportionality will be declared if the 90% CI for the slope parameter 'b' lies entirely within the critical region (0.80, 1.25) using the maximal dose ratio I = 3 (highest dose/lowest dose), a lower equivalence limit of 0.80, and an upper equivalence limit of 1.25.

Additionally, the geometric means for the primary PK parameters between adjacent dose levels will be compared using an analysis of covariance (ANCOVA) model including dose, gender and weight as fixed effects for subjects who receive one administration at a given dose interval. Geometric mean ratios for adjacent administrations (higher

dose/lower dose) and corresponding 90% CI will be presented. PER977 and BAP exposure parameters ( $C_{max}$ ,  $AUC_{(0-inf)}$ , and  $AUC_{(0-last)}$ ) will be plotted versus dose on linear and log-log scales for subjects who receive one administration at a given dose level using a scatterplot with individual exposures, regression line and corresponding confidence bands.

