2.2 Secondary Objectives

The secondary objectives of this study are:

- To evaluate the safety and tolerability of ciraparantag 60 mg (100 mg ciraparantag acetate), 120 mg (200 mg ciraparantag acetate), and 30 mg (50 mg ciraparantag acetate), and additional cohorts if necessary administered approximately 3 hours after 10 mg apixaban administration at steady state.

- To assess the PK characteristics of apixaban and of ciraparantag and its primary metabolite, 1,4-bis(3-aminopropyl) piperazine (BAP).

[figure not shown]
3 Study Design and Methods

This is a randomized, single-blind, placebo-controlled assessment of the efficacy and safety of ciraparantag administered to healthy volunteers measuring clotting times using WBCT. All subjects will undergo screening up to 36 days prior to enrollment.

Randomization will take place on Day 4 after administration of apixaban. Subjects will be enrolled sequentially into one of up to three cohorts. If the Screening visit takes place within 3 weeks prior to check-in, the check-in procedures may be modified to exclude redundant procedures at the discretion of the Investigator. There will be a safety review after completion of treatment in one cohort and before initiation of treatment in the subsequent cohort.

Subjects (n=16 per cohort) will be randomized in a 3:1 ratio to receive ciraparantag or placebo (saline for injection). [Figure 1](#) depicts the experimental design.

Figure 1 Dose Schema

All subjects will receive 10 mg apixaban for 3.5 days (twice daily Q12 on Days 1-3 and once on the morning of Day 4). On Day 4, approximately 3 hours after administering apixaban, study drug or placebo will be intravenously administered. Study drug will be administered only to those subjects who have a minimum increase in clotting time of 20% (as measured by WBCT) above Day 1 pre-apixaban baseline levels at the pre-study drug time point on Day 4 (i.e., 2.75 hours post-apixaban). Any subject who does not have a minimum increase in clotting time of 20% above Day 1 pre-apixaban baseline levels at the pre-study drug time point on Day 4 will be discontinued from the study and replaced. At approximately 3 hours following apixaban a single IV dose of study drug (ciraparantag or placebo) will be administered.

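### The dose-proportionality rule puts exposure-ratio limits of 0.80 and 1.25 directly on the power-model slope, and Protocol 9.6 states a dose ratio of 3 when the planned doses span 4-fold

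*SAP*

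**What the plan says.** Both documents fit log(PK parameter) = a + b·log(dose) to AUC(0-inf), AUC(0-last) and Cmax of ciraparantag and of its metabolite BAP. Under SAP 4.6.3, proportionality is declared if the 90% CI for b "lies entirely within the critical region (0.80, 1.25"). The SAP names no dose ratio and does not say where the limits come from.

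Protocol 9.6 prints the same slope region and gives its basis: "using the maximal dose ratio I = 3 (highest dose/lowest dose), a lower equivalence limit of 0.80, and an upper equivalence limit of 1.25".

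The planned doses appear in Protocol section 2 as "ciraparantag 60 mg (100 mg), 120 mg (200 mg), and 30 mg (50 mg") and identically in SAP 2.2. The bracketed figures are the acetate-salt equivalents.

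Protocol 1.2.4 describes the same kind of test in PER977-02-001, over a 24-fold dose range. There the CI for one slope is compared with a different region; the results "were completely above the predefined (0.9298, 1.0702) critical region".

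**The concern.** A dose ratio and a pair of equivalence limits are the inputs for deriving a slope region. Protocol 9.6 lists all three inputs and then prints the two equivalence limits unchanged as the slope region, so the dose ratio does no work. The stated ratio is also wrong for the planned doses: pairs among 30, 60 and 120 mg have ratios of 2 or 4, never 3.

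At stake is a pre-specified yes/no statement about PK linearity. If the region is too wide for the dose range, exposure that departs from proportionality by more than the stated limits can be labelled proportional. BAP is the likelier place for this. Protocol 1.2.4 reports BAP slopes 12% to 48.3% above unity in PER977-02-001, a range that includes the slopes where the printed rule is too lenient. Ciraparantag itself was approximately proportional in that study.

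**Working it through.** **Conversion.** Under the power model, exposure at dose D is e^a·D^b, so dose-normalised exposure is e^a·D^(b−1). Between the highest and lowest dose, with ratio r, the dose-normalised exposure ratio is r^(b−1). Requiring 0.80 < r^(b−1) < 1.25 gives

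1 + ln(0.80)/ln(r) < b < 1 + ln(1.25)/ln(r).

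**Check against the earlier study.** For PER977-02-001, r = 360/15 = 24 and ln 24 = 3.178. The region is 1 − 0.2231/3.178 = 0.9298 to 1 + 0.2231/3.178 = 1.0702. This matches Protocol 1.2.4 to four decimals, so that study used this formula with limits 0.80 and 1.25.

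**Attempt to reproduce this study's region.**

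| Dose ratio r | Converted slope region |
|---|---|
| 3 (stated in Protocol 9.6) | 0.797 to 1.203 |
| 4 (planned doses, 120/30) | 0.839 to 1.161 |
| Printed in both documents | 0.80 to 1.25 |

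The printed region follows from neither ratio. No single r gives both limits: 0.80 needs r = 0.80^(1/−0.20) = 3.05, and 1.25 needs r = 1.25^(1/0.25) = 2.44. A converted region is also symmetric about 1, because ln(1.25) = −ln(0.80); the printed one is not. Correcting the 3 to 4 alone would change nothing, since the printed limits do not depend on it.

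**Printed limits translated back.** Over a 4-fold range, slopes of 0.80 and 1.25 mean exposure ratios of 4^(−0.20) = 0.758 and 4^(0.25) = 1.414.

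**Effect on the declaration.** Inputs: 16 subjects per cohort randomised 3:1 (Protocol 3.1), hence 12 active subjects at each of 30, 60 and 120 mg. Sxx = 12 × 2 × (ln 2)² = 11.53, with 36 − 2 = 34 df and t = 1.691. The documents give no between-subject CV, so a range is assumed, with log-scale SD = √ln(1 + CV²). The OLS slope and its 90% CI were simulated, with at least 1,000,000 draws per setting. A 90% CI rule is two one-sided 5% tests, so the pass rate at or beyond a limit should be at most 5%.

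Chance of declaring proportionality when the true exposure ratio is at or outside 0.80 to 1.25:

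| True slope (exposure ratio), region used | CV 15% | 20% | 25% | 30% | 40% |
|---|---|---|---|---|---|
| 1.161 (1.25), printed | 63% | 44% | 33% | 25.5% | 12% |
| 1.161, converted with r = 3 | 24% | 17% | 14% | 11.5% | 4% |
| 1.161, converted with r = 4 | 5% | 5% | 5% | 3% | 0.3% |
| 1.20 (1.32), printed | 30% | 21% | 17% | 14% | 8% |
| 0.839 (0.80), printed | 22% | 16% | 13% | 11% | 7% |

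At true slopes of 1.25 and 0.80 the printed rule passes 5.0% for CVs of 15% to 30% and 3.8% at 40%. The excess is therefore confined to slopes of about 1.16 to 1.25 and 0.80 to 0.84.

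**Price of conversion.** Chance of passing when the drug is exactly proportional (slope 1.00):

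| Region | CV 15% | 20% | 25% | 30% | 40% |
|---|---|---|---|---|---|
| Printed | 99.8% | 95% | 81% | 62% | 23.5% |
| Converted with r = 4 | 95% | 71% | 40% | 16% | 0.7% |

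The cause is the CI width. The expected half-width is about 1.691 × SD/√11.53, or 0.12 at CV 25% and 0.19 at CV 40%, against a converted region only 0.161 wide on each side of 1.

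**The case against.** The strongest reply concerns the SAP. Read alone, SAP 4.6.3 simply sets a margin on the slope: it states no exposure-ratio limits and no dose ratio, so it contains no arithmetic to get wrong. Against that margin the test holds its level, with 5% or less at slopes of 0.80 and 1.25. On this view the excess pass rates only show that the margin is wider than another one that could have been chosen. The protocol leaves analysis detail to the SAP, a slope margin could be a deliberate choice, and the converted region has poor power with 12 subjects per dose.

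Part of this stands. The ratio error belongs to the protocol alone, the sizes depend on assumed CVs, and the power cost is real. At the lower limit, the gap from the protocol's own ratio is only rounding (0.797 against 0.80).

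It does not rescue the rule. The SAP uses the protocol's region without a new rationale, and SAP 4.11 lists only the replacement of Tukey's procedure by Dunnett's test as a change. The meaning of 0.80 and 1.25 is therefore still the one given in Protocol 9.6, and the printed region does not deliver it.

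The consequences are limited. The dose-decision process rests on other data: "Review of WBCT results, AEs, clinical laboratory tests, and ECG data will be conducted by a group" in Protocol 5.9, with no mention of PK. SAP 4.6.3 also reports the slope with its CI, and "pairwise comparisons by analyte including the dose ratio (%), exposure ratio (%), and 90% confidence interval will be presented", so a reader can apply another margin.

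**Conclusion.** The concern holds on both parts. In both documents the slope region is the unconverted pair of exposure-ratio limits. In Protocol 9.6 the stated ratio of 3 also disagrees with the planned 4-fold range. The conversion is exact arithmetic and is confirmed by the sponsor's own region for PER977-02-001.

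The result is a rule that accepts exposure ratios of 0.758 to 1.414 while naming 0.80 to 1.25. At the upper edge of the intended region, the chance of a wrong declaration is 12% to 63% instead of at most 5%. Those rates assume 12 evaluable active subjects per dose, the planned doses, log-normal exposure and CVs of 40% down to 15%. The point should be fixed, but its reach is a PK label, most plausibly for BAP. The primary WBCT analysis is untouched.

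**What to change.** In SAP 4.6.3 and Protocol 9.6, define the slope region as (1 + ln 0.80/ln r, 1 + ln 1.25/ln r), where r is the ratio of the highest to the lowest dose actually administered. For 30 to 120 mg this is (0.839, 1.161). Reconcile the stated ratio of 3 in Protocol 9.6 with the planned doses. Have the region recomputed if doses or cohorts change, since the objectives allow additional cohorts and Protocol 5.9 allows doses other than those planned. Converting the limits but leaving r = 3 would not be enough, as the pass rates at slope 1.161 show.

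If the sponsor prefers the wider margin because of the power loss, the alternative is to keep (0.80, 1.25) as an explicit slope criterion. The text should then drop the reference to exposure-ratio limits of 0.80 and 1.25, and state that over a 4-fold range the criterion corresponds to exposure ratios of 0.758 to 1.414.

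Either route takes about one line in each document and no new data. Conversion also brings the power loss tabulated above. If it is chosen, the report should give the slope and CI prominence and should not read a failed declaration as evidence of non-proportionality.
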